4.1 Type of trial

Double blind randomized trial.

4.2 Trial design

4.2.1 Baseline survey and screening

This trial will take place in the two primary schools (Bagamoyo School and Piki School) in Pemba, Tanzania, which have been found to have a high prevalence of hookworm in previous studies. Among those children for whom informed consent is obtained, each participant will receive an empty container at school, which they return the following day with a stool sample. Stool samples will be collected and transported by car to the central laboratory. Two stool samples will be collected from each participating individual on different days, to adequately cover the egg shedding cycle of 24-48 hours, until a total of 180 hookworm-infected participants have been identified, preferable with *A. lumbricoides* and/or *T. trichiura* co-infections (Fig. 1). The prevalence for hookworm infected individuals is expected to be between 20% and 40% [17, 49, 50], hence we anticipate screening around 500-1,000 individuals to reach the total number of participants. The number of screened individuals will depend on the prevalence of the parasite.

The Kato-Katz technique will be used for the quantitative assessment of STH infections. Two stool samples will be collected from each participant before treatment and from each sample

duplicate Kato-Katz thick smears (41.7 mg each) will be prepared [51]. The slides will be analysed under a microscope by experienced technicians and a subsequent independent quality control of sample results (10%) will be conducted. Results are considered correct if the following tolerance margin is not exceeded: (i) No difference in presence/absence of hookworm, *A. lumbricoides* and *T. trichiura*, (ii) Egg counts are ± 10 eggs for counts ≤ 100 eggs or $\pm 20\%$ for counts > 100 eggs (for each species separately) [52]. In case discrepancies above the tolerance margin are noted in one or more slides, all slides are re-read by the local technicians. The new results are discussed, so that in case of discordant results, slides can be re-evaluated to reach consensus. Infection intensity expressed as the arithmetic and geometric mean egg count per gram of stool (EPG) will be calculated for each treatment arm.

[figure not shown]

Figure 1: Mebendazole efficacy study-flow.

All stool samples will be prepared and analysed in the Public Health Laboratory Ivo de Carneri on Pemba, United Republic of Tanzania. All quadruplicate Kato-Katz thick smears will be microscopically analysed within the first 60 minutes and will then be destroyed within a few days (after passing the quality control). Also, two aliquots (about 1 g of stool each) of positive samples will be stored in ethanol. One aliquot will remain in Pemba as a “back-up”

sample and the other aliquot will be transported to the Swiss Tropical Public Health Institute for subsequent DNA extraction, diagnostic and assessment of drug resistance-associated single-nucleotide polymorphisms. Upon successful PCR analysis, the aliquot which was stored in Pemba will be destroyed. Finally, a Harada Mori culture will be prepared from one of the stool samples of each child at baseline and at follow-up to extract hatched larvae. Larvae will be stored in ethanol and will subsequently undergo the same process as the previously mentioned stool aliquots.

Among those participants who tested positive for hookworm, the second stage of screening involves a physical examination and will occur one to three days before treatment is scheduled to begin. At baseline the medical history of STH-infected participants will be assessed at school during clinical examination carried out by the study clinician. Additionally, during this clinical examination, haemoglobin levels will be detected using HemoCue conducted by nurses to exclude severely anaemic participants (below 80 g/l Hb according to WHO definition). In all girls, the clinician will assess the possibility of pregnancy by asking if menarche has occurred. If menarche has occurred and thus pregnancy cannot be ruled out, the participant will be excluded from the trial, but will still be given the option of receiving only placebo to avoid any stigmatization.

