Study Objectives	To assess the efficacy and safety of two dose regimens of mebendazole: i) 100 mg solid tablets twice a day for 3 days, and ii) one dose of 500 mg solid tablets of mebendazole in participants aged 6-12, inclusive, infected with hookworm. The primary objective of the trial is to assess the cure rate (CR) of a 3-day regimen of mebendazole against hookworm and a single dose mebendazole treatment. The secondary objectives are to determine if the multi-dose regimen is superior to the single dose regimen, evaluate the efficacy against concomitant soil-transmitted helminth infections, and assess the safety of both mebendazole regimens.
Study -design	Double blind, randomized trial (both participants and outcome assessors are blinded)
Study product intervention	Mebendazole
Comparator(s)	None
Key inclusion / Exclusion criteria	Inclusion: individuals aged between 6 and 12 with a hookworm infection, absence of major systemic illnesses, written informed consent signed by parents/caregivers; and oral assent by the participants. Exclusion: Menarche, any abnormal medical conditions or chronic disease, negative diagnostic result for hookworm, no written informed consent

Primary Endpoints	CR against hookworm
Secondary Endpoints	Egg reduction rate (ERR, based on geometric means) against hookworm, CR/ERR against A. lumbricoides and T. trichiura , safety
Exploratory Endpoints	
 • Sensitivity of Kato Katz compared to quantitative polymerase chain reaction assays • Prevalence of mebendazole genetic resistance markers • Prevalence of STH species
Interim Analyses	None
Study Duration	12 weeks total; up to 8 weeks per participant
Schedule	07/2017 of first-participant in (planned) 10/2017 of last-participant out (planned)

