The primary objective of the study is to assess the CR (*i.e.* conversion from being egg positive pre-treatment to egg negative post-treatment) of two different mebendazole regimens against hookworm in children (6 - 12 years old): (i) 100 mg of mebendazole twice a day for 3 days and (ii) 500 mg of mebendazole single dose. Thus, the **primary endpoint** of the study is the CR of these two regimens of mebendazole against hookworm.

Additional **secondary endpoints** are (1) the ERR of these two regimens against hookworm, (2) the CR and ERRs of both mebendazole regimens against concomitant soil-transmitted helminth infections, and (3) the safety of both mebendazole regimens. **Exploratory endpoints** include comparison of the sensitivity of Kato Katz to quantitative polymerase chain reaction assays, prevalence of genetic resistance markers among participants, and distribution of hookworm species among participants.

4. Methodology

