4.2.2 Assessment of efficacy after treatment

The efficacy of the treatment in participants will be determined 14-21 days post-treatment by collecting another two stool samples and microscopically examined for STH using duplicate Kato-Katz thick smears, creating a total of four slides for this time point assessment. Kato-Katz is the standard method used to diagnose STH and is the reference standard for much of the literature reporting anti-helminthic treatment efficacy. Kato-Katz thick smears are not as sensitive as more recently developed methodologies, such as quantitative PCR, and slides have to be read within a strict window for accurate results. Appendix 1 includes instructions that will be followed for Kato-Katz preparation and analysis.

Individuals will be considered hookworm negative if EPG < 100 (total of the four slides) and/or if only one Kato-Katz thick smear slide with more than one hookworm egg. EPG will be assessed by adding up the egg counts from the quadruplicate Kato-Katz thick smears and multiplying this number by a factor of six. Geometric and arithmetic mean egg counts will be calculated for the two treatment arms before and after treatment to assess the corresponding ERRs.

Additionally, an aliquot from each participant stool sample positive for any of the soil-transmitted helminths (*A. lumbricoides*, *T. trichiura* or hookworms) at either baseline or follow-up survey, will be stored at Public Health Laboratory Ivo de Carneri in absolute ethanol. Aliquots will be shipped to the Swiss Tropical Public Health Institute (Basel,

Switzerland) to undergo DNA extraction and quantitative polymerase chain reaction (PCR) analysis to perform molecular genotyping for drug resistance-associated single-nucleotide polymorphisms studies. At the end of the study all participants in whose post-treatment samples we still find hookworm eggs will be contacted at school with their test results and treated with albendazole (400 mg single dose), the current local standard drug against hookworm.

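### Stool is kept for PCR only when Kato-Katz is positive for some helminth, so hookworm sensitivity of Kato-Katz against PCR cannot be estimated without upward bias

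*Combined protocol and SAP*

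**What the plan says.** The synopsis lists among the exploratory endpoints "Sensitivity of Kato Katz compared to quantitative polymerase chain reaction assays". Section 3 repeats it as "comparison of the sensitivity of Kato Katz to quantitative polymerase chain reaction assays". Neither place names a species, a time point or a unit of analysis (stool or child), and section 7.3 describes no analysis of this endpoint.

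Storage is described twice. Section 4.2.1 states that "two aliquots (about 1 g of stool each) of positive samples will be stored in ethanol", without saying positive for what. Section 4.2.2 keeps "an aliquot from each participant stool sample positive for any of the soil-transmitted helminths" and specifies the time points: "at either baseline or follow-up survey, will be stored at Public Health Laboratory Ivo de Carneri in absolute ethanol". No section stores stools that are negative for all three species, draws a sample of them, or plans a correction for their absence.

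Section 4.2.1 adds one source of material that does not depend on the Kato-Katz result: "a Harada Mori culture will be prepared from one of the stool samples of each child at baseline and at follow-up". The hatched larvae "will subsequently undergo the same process as the previously mentioned stool aliquots".

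Section 4.2.2 also gives the protocol's own view of the two methods: "Kato-Katz thick smears are not as sensitive as more recently developed methodologies, such as quantitative PCR".

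**The concern.** Sensitivity against PCR is the share of PCR-positive stools that Kato-Katz also finds. Its denominator includes the stools that are PCR-positive and Kato-Katz-negative. The storage rule selects on the Kato-Katz result, which is the test under evaluation, and so removes most or all of those stools. This is partial verification, and the error runs one way: the estimate is too high. By its own statement that Kato-Katz is the less sensitive method, the protocol expects such missed stools to exist.

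Two things are at stake. An inflated sensitivity could be published from a trial that followed its plan exactly. The trial would also lose most of the evidence on how many children classed as cured still carry infection detectable by PCR, which matters for reading the cure rates. The loss cannot be repaired later. Negative stools are never preserved, and the synopsis and section 10.2 provide for all samples to be destroyed after the study.

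**Working it through.** The plan states no sensitivity, precision or sample size for this endpoint, so there is no figure to reproduce.

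**Inputs from the protocol**
- Storage rule: positive for at least one of the three helminths, at both time points (section 4.2.2).
- Randomised children: 180, two stools each at follow-up (sections 4.2.2 and 7.2).
- Planned cure rates: 20% and 40% (section 7.2).
- Screening: 500 to 1,000 children to find 180 positives (section 4.2.1).

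**Inputs assumed, because the documents do not give them**
- s, the true sensitivity of Kato-Katz for hookworm against PCR: 60% and 80%.
- f, the share of missed hookworm stools (PCR-positive, Kato-Katz-negative) that are kept: 0 to 1.

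**Formula.** Of all hookworm PCR-positive stools, a share s is Kato-Katz-positive and all of these are kept. A share 1 − s is Kato-Katz-negative, and a fraction f of these is kept. Hence

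apparent sensitivity = s / (s + (1 − s) × f).

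| f | s = 60% | s = 80% |
|---|---|---|
| 0 | 100% | 100% |
| 0.10 | 0.60/0.64 = 93.8% | 0.80/0.82 = 97.6% |
| 0.25 | 0.60/0.70 = 85.7% | 0.80/0.85 = 94.1% |
| 0.50 | 0.60/0.80 = 75.0% | 0.80/0.90 = 88.9% |
| 0.75 | 0.60/0.90 = 66.7% | 0.80/0.95 = 84.2% |
| 1 (all stools kept) | 60% | 80% |

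**What f is under each reading of the rule**
- *Any helminth, pooled.* Every stored stool is Kato-Katz-positive, so f = 0 and the estimate is 100% whatever s is.
- *Hookworm, section 4.2.2 rule.* f is the share of missed hookworm stools in which Ascaris or Trichuris was seen, so it lies above 0 but below 1 unless every missed stool is co-infected.
- *Hookworm, if the positive samples of section 4.2.1 mean hookworm-positive.* f = 0 at baseline.
- *Ascaris and Trichuris.* Stools kept because another species was seen include some in which these two were missed. Sensitivity can be estimated within those stools, but not beyond them.

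**How many stools are affected**
- Baseline: 500 − 180 = 320 to 1,000 − 180 = 820 screened children would be hookworm-negative.
- Follow-up, children classed as cured: 90 × 0.20 + 90 × 0.40 = 18 + 36 = 54, with 54 × 2 = 108 stools.
- Follow-up, children still positive: 180 − 54 = 126. Each has at least one positive stool and so at most one negative stool, giving up to 126 more.
- Ceiling on hookworm-negative follow-up stools: 108 + 126 = 234 of 360.

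**The case against.** The strongest case on the other side has four parts.

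1. *Hookworm-negative stools do reach PCR.* This is correct. Section 4.2.2 keeps stools with another helminth, and section 4.2.1 prefers co-infected children. A reader might infer that sensitivity cannot be estimated at all, or that each species is forced to 100%. The documents do not support either. The 100% result holds only for a pooled any-helminth measure, which the plan does not name, or for hookworm at baseline if section 4.2.1 is read narrowly. An analysis restricted to stools in which another helminth was seen would give a hookworm sensitivity for co-infected stools. The plan does not specify that restriction, and the result would not describe hookworm in general.

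2. *Harada Mori larvae come from each child whatever the Kato-Katz result.* This stands in part. It gives some molecular data on Kato-Katz-negative children, including those classed as cured. It covers one stool per child per time point, and only where larvae hatch. A culture without larvae does not show that the stool was PCR-negative, so the missed stools remain uncounted.

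3. *A hookworm-negative child's stool may already be stored.* This is also correct. Section 4.2.2 classes a child as negative below 100 EPG, and/or when only one slide has more than one egg, so a stool with few eggs could be kept. Against that definition of negative, f is higher and the bias smaller.

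4. *The endpoint is exploratory, and section 4.2.2 links the PCR to resistance genotyping.* This limits the importance of the point. Section 4.2.1 nevertheless lists diagnostic use, and the endpoint is stated twice. A reader might also infer that the cure-rate comparison is undermined. It is not: that comparison uses Kato-Katz in both arms and needs no PCR result.

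**Conclusion.** The endpoint and the storage rule do not fit together. Followed as written, the plan yields a hookworm sensitivity that is biased upward, because missed infections enter only when another helminth was seen in the same stool. Over the assumed range of f from 0.50 down to 0.10, a true 60% would appear as 75% to 94%, and a true 80% as 89% to 98%. The direction of the bias needs only that some missed stools are discarded; its size rests entirely on assumed s and f. Sensitivity for Ascaris and Trichuris is estimable only within stools kept for another species.

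The consequence is confined to an exploratory endpoint. The primary comparison and the sample size are unaffected. It is still worth correcting before collection starts, since the discarded stools cannot be recovered.

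**What to change.** Choose one of the following.

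- *Restate the endpoint* in the synopsis and section 3 as PCR confirmation and species typing among Kato-Katz-positive stools. This is a wording change and costs nothing.
- *Store one aliquot of every follow-up stool from randomised children*, whatever the Kato-Katz result, and estimate sensitivity on that set. This is 180 × 2 = 360 aliquots in total. At the planned cure rates it is at most about 234 more than now, and fewer where another helminth or a low egg count already leads to storage. Counting only the two stools of each child classed as cured (108) does not give an upper limit, because children who remain positive can also have one negative stool. The estimate would describe Kato-Katz after treatment, not at screening.
- *Store a random sample of Kato-Katz-negative stools* with a recorded sampling fraction, and weight each by the inverse of that fraction. This needs fewer PCR runs and can cover both time points, at the price of wider confidence intervals.

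Under any option, align the storage wording of section 4.2.1 with that of section 4.2.2. If sensitivity is kept, add to section 7.3 the species, time point, unit of analysis and the Kato-Katz rule for a positive result.

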4.2.2 Assessment of efficacy after treatment

The efficacy of the treatment in participants will be determined 14-21 days post-treatment by collecting another two stool samples and microscopically examined for STH using duplicate Kato-Katz thick smears, creating a total of four slides for this time point assessment. Kato-Katz is the standard method used to diagnose STH and is the reference standard for much of the literature reporting anti-helminthic treatment efficacy. Kato-Katz thick smears are not as sensitive as more recently developed methodologies, such as quantitative PCR, and slides have to be read within a strict window for accurate results. Appendix 1 includes instructions that will be followed for Kato-Katz preparation and analysis.

Individuals will be considered hookworm negative if EPG < 100 (total of the four slides) and/or if only one Kato-Katz thick smear slide with more than one hookworm egg. EPG will be assessed by adding up the egg counts from the quadruplicate Kato-Katz thick smears and multiplying this number by a factor of six. Geometric and arithmetic mean egg counts will be calculated for the two treatment arms before and after treatment to assess the corresponding ERRs.

Additionally, an aliquot from each participant stool sample positive for any of the soil-transmitted helminths (*A. lumbricoides*, *T. trichiura* or hookworms) at either baseline or follow-up survey, will be stored at Public Health Laboratory Ivo de Carneri in absolute ethanol. Aliquots will be shipped to the Swiss Tropical Public Health Institute (Basel,

Switzerland) to undergo DNA extraction and quantitative polymerase chain reaction (PCR) analysis to perform molecular genotyping for drug resistance-associated single-nucleotide polymorphisms studies. At the end of the study all participants in whose post-treatment samples we still find hookworm eggs will be contacted at school with their test results and treated with albendazole (400 mg single dose), the current local standard drug against hookworm.

4.3. Measure to minimize bias

Study participants eligible for treatment will be randomly assigned to one of the two treatment arms using a computer-generated stratified block randomization code. The random allocation sequence with varying random blocks of four or eight and stratified by 2 levels of baseline infection intensity (light: 1-1999 EPG, and moderate plus heavy: ≥ 2000 EPG hookworm infections) will be provided by a statistician. Both treatment arms will have an equal number of participants with light infection intensity, although the number of light versus moderate/heavy infections are not expected to be equal in each arm, depending on the distribution of infection intensity in the recruited cohort. The codes will be held in a locked cabinet at the Swiss Tropical and Public Health Institute. A copy of this code will be kept in a sealed envelope by one of the co-investigators (will only be unblinded in case there is a serious adverse event, determined by the principal investigator upon consultation with the co-investigators). The blinding will be maintained throughout the trial until data entry and processing are complete and the data have been verified. Following release of the final data, the randomization codes will be released.

4.4. Study duration and duration of subject participation

The trial will last twelve weeks with each participant's involvement lasting up to eight weeks. The screening for the baseline will start three weeks prior to the treatment. Follow up screening will take place 14-21 days post-treatment and last for about three weeks. Schedules of visits are summarized below.

4.5. Schedule of visits

Table 2 briefly presents the distribution of tasks along the trial. Further detail is available in Appendix 2.

Table 2. Schedule of visits during treatment period.

Screening							Follow-up
- 21 to -1	-3 to -1	D1	D2	D3	D4	D5	14 to 21 days
		Hours					

	days	days	0	3	10	0	3	10	0	3	10	0	0	
Diagnosis (stool examination)	X													X
Informed consent	X													
Demographics	X													
Medical History		X												
Administration of treatment/placebo			X		X	X		X	X		X			
Physical Examination, including menarche and anemia assessments		X												
Capturing AEs/ SAE				X		X	X		X	X		X	X	
Administration of albendazole (still infected at follow-up)														X

5. Selection of the trial subjects

5.1 Recruitment

The study will be carried out in children (age: 6-12 years) in one primary school on Pemba, United Republic of Tanzania in areas endemic for hookworm [17, 21, 49, 50, 53].

The parents/caregivers of participants will be invited to participate in an information meeting to explain the purpose and procedures of the study, including potential benefits and risks. Parents/caregivers will be encouraged to ask questions in an open discussion forum. During this session, parents will be informed of preventive actions they can take to help protect their children from acquiring hookworm and other STH infections in the future (e.g., wearing shoes, hand washing procedures).

Those parents/caregivers and their children who are interested in the study will be invited to complete the process of informed consent. See section 9.3 for details on obtaining informed consent. Only those participants who have written informed consent will be assessed for study eligibility criteria during screening procedures.

5.2 Inclusion criteria

1. Written informed consent signed by parents and/or caregiver; and oral assent by participant.
2. Able and willing to be examined by a study physician at the beginning of the study.
3. Able and willing to provide two stool samples at the beginning (baseline) and approximately three weeks after treatment (follow-up).

4. Positive for hookworm eggs in the stool (≥ 100 EPG and at least two Kato-Katz thick smears slides with more than one hookworm egg).
5. Absence of major systemic illnesses, e.g. diabetes, severe anemia (HB<8.0 g/l) as assessed by a medical doctor at school, upon initial clinical assessment.
6. No known or reported history of chronic illness as cancer, diabetes, chronic heart, liver or renal disease.
7. No recent anthelmintic treatment (within past 4 weeks).
8. No known allergy to study medications (mebendazole and albendazole).

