5.3. Exclusion criteria

1. No written informed consent by parents and/or caregiver; no oral assent by participant.
2. Menarche, based on self-report
3. Presence of major systemic illnesses, e.g. diabetes, severe anemia (HB<8.0 g/l) as assessed by a medical doctor, upon initial clinical assessment.
4. History of acute or severe chronic disease.
5. Recent use of anthelmintic drug (within past 4 weeks).
6. Attending other clinical trials during the study.
7. Negative diagnostic result for hookworm eggs in the stool (< 100 EPG (total of the four slides) and/or only one Kato-Katz thick smear slide with more than one hookworm egg).

Participants who were diagnosed with a STH infection, but who were excluded from the study due to one or several of the above-mentioned exclusion criteria, including withdrawals, will be offered standard anthelmintic treatment (albendazole).

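### The haemoglobin limit for severe anaemia is 8.0 g/l in the eligibility criteria but 80 g/l in the screening procedure, a tenfold contradiction in a safety exclusion

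*Combined protocol and SAP*

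**What the plan says.** The limit for severe anaemia appears in three places.

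- Section 5.2, inclusion criterion 5, requires the absence of major systemic illness and gives as one example "severe anemia (HB<8.0 g/l) as assessed by a medical doctor at school".
- Section 5.3, exclusion criterion 3, mirrors this with "severe anemia (HB<8.0 g/l) as assessed by a medical doctor, upon initial clinical assessment".
- Section 4.2.1 describes the screening step. There, "haemoglobin levels will be detected using HemoCue conducted by nurses", and the stated purpose is "to exclude severely anaemic participants (below 80 g/l Hb according to WHO definition").

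Table 2 in section 4.5 has a single row for this assessment, "Physical Examination, including menarche and anemia assessments", marked in the column for one to three days before treatment. The three statements therefore concern one pre-treatment decision. The synopsis mentions major systemic illness but gives no haemoglobin figure, so it does not settle the matter.

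**The concern.** Two limits for one decision cannot both be followed over the range between them. The lower figure stands in the numbered eligibility criteria, the list against which enrolment is normally checked and monitored. The higher figure stands in the description of the measurement itself.

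Three features of the plan add weight.

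- **Two roles are involved.** Nurses take the reading (section 4.2.1) and a medical doctor judges the criterion (sections 5.2 and 5.3). One written limit is what keeps them consistent.
- **The classification changes what happens to the child.** Under section 5.3 an excluded child with a soil-transmitted helminth infection is offered albendazole. An enrolled child is randomised to a blinded mebendazole regimen and, under section 4.2.2, receives albendazole at the end of the study if hookworm eggs persist.
- **There is no data and safety monitoring board** (section 10.4). In a trial of children aged 6 to 12, screening for eligibility is one of the main safeguards.

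Section 8.1 commits the trial to following the protocol. For a child in the disputed range, either decision departs from one part of it.

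**Working it through.** **Inputs**

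| Source | Printed rule | Unit |
|---|---|---|
| Section 5.2, criterion 5 | severe anaemia if Hb < 8.0 | g/l |
| Section 5.3, criterion 3 | severe anaemia if Hb < 8.0 | g/l |
| Section 4.2.1 | severe anaemia if Hb < 80 | g/l |

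**Step 1: ratio.** The units are identical, so the figures can be compared directly: 80 / 8.0 = 10.

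**Step 2: unit conversion.** With 1 g/dl = 10 g/l:

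- 8.0 g/l = 8.0 / 10 = 0.8 g/dl
- 80 g/l = 80 / 10 = 8.0 g/dl

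The digits 8.0 in the criteria match the screening limit if that limit is expressed in g/dl. This points to a unit slip as the likely origin. It does not remove the contradiction, because the unit actually printed is g/l in all three places.

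**Step 3: apply each printed limit to example readings.**

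| Hb (g/l) | Section 4.2.1 (< 80) | Hb limit in 5.2 and 5.3 (< 8.0) | Agree? |
|---|---|---|---|
| 7 | excluded | excluded | yes |
| 8 | excluded | not excluded | no |
| 20 | excluded | not excluded | no |
| 50 | excluded | not excluded | no |
| 79 | excluded | not excluded | no |
| 80 | not excluded | not excluded | yes |
| 90 | not excluded | not excluded | yes |

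The printed limits disagree for every reading from 8.0 up to, but not including, 80 g/l, and agree everywhere else.

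**Step 4: number of children affected.** This cannot be calculated. The protocol gives neither a haemoglobin distribution nor a prevalence of anaemia for the population to be screened.

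**The case against.** The strongest reply is that the passages work together. Section 4.2.1 is part of the protocol and is the only text that says how haemoglobin is measured and to what end. If staff follow it, a child below 80 g/l is kept out whatever the criteria list says. Such a child would enter only if the list were applied and the screening procedure ignored. This stands as a statement about likelihood. It does not answer the contradiction, since eligibility checklists are often built from the numbered criteria.

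Second, in sections 5.2 and 5.3 severe anaemia is only an example of major systemic illness, judged by a doctor, and exclusion criterion 4 offers a further route. A child in the disputed range could still be excluded on clinical judgement. This also stands, and it narrows the claim: such a child is not excluded by the printed haemoglobin limit, which is not the same as being certain to enrol.

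Third, a unit slip is more plausible than two intended rules, the number affected is unknown and could be zero, and the primary endpoint, sample size and analysis are untouched. All of this is correct and bears on the practical effect. None of it makes the limits agree.

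Finally, the case report form is not among the documents, so nothing can be said about the limit it carries. That is a reason to check it, not to assume that it is wrong.

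**Conclusion.** The concern holds. One safety threshold is printed with two values that differ exactly tenfold in the same unit, and the protocol does not reconcile them. The conclusion rests on reading the limits as printed and on treating the three statements as one pre-treatment assessment, which Table 2 supports. How many children would be misclassified depends on which text the site follows and on haemoglobin values that the documents do not give.

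This must be corrected before screening because it governs which children may receive study drug. It has no bearing on the power calculation or the planned comparisons of cure and egg reduction rates. No view is taken here on which value is right.

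**What to change.** Before screening starts, the sponsor and the study's medical staff should decide the intended limit and state it once, as one figure with one unit, in section 4.2.1, inclusion criterion 5 and exclusion criterion 3. Cross-referring two of these places to the third would prevent a recurrence.

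Section 7.4 says that range and consistency checks will be programmed. The haemoglobin field on the case report form, any eligibility checklist and the database check should be confirmed against the agreed figure and unit.

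Because an eligibility criterion changes, this should go through the documented amendment and ethics committee approval described in section 8.1. The textual cost is about one line in each of three places, plus the check of the form and database. The target of 180 participants, the endpoints and the analysis need no change.
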